Protocol Number: ICM-BC-02

Date: Oct 27, 2021

Version:18.1

ICE3 Study – Clinical Study Synopsis

Page 1 of 3

Cryoablation of Low-Risk Breast Cancers less than 1.5 cm: An evaluation of local recurrence (Ice3 Trial) – ICMBC-02

Study Plan- Synopsis

Study Title	Cryoablation of Low-Risk Breast Cancers less than 1.5 cm: An evaluation
,	of local recurrence (Ice3 Trial)
Investigational	PROSENSE™
Device	
Study Sites and	212 subjects/ 19 sites
Participants	
Device Description	IceCure Medical's PROSENSE™ cryogenic system (also branded as ICESENSE3™) is intended for cryogenic destruction of tissue (utilizes Liquid Nitrogen) during surgical procedures (minimally invasive imageguided), by the application of extreme cold temperatures.
	The PROSENSE™ system has FDA clearance (K183213) for use as a cryosurgical tool in the fields of general surgery (including breast fibroadenomas), dermatology, neurology, thoracic surgery, ENT, gynecology, oncology, proctology, and urology.
Study Design	Multi-centered, single arm, non-randomized clinical trial. Patients will undergo imaging by mammography, ultrasound and breast MRI (optional) pre-registration to ensure eligibility. All fully eligible and registered patients will then be treated with cryoablation therapy followed by 6 month and annual mammograms and physical examinations for 5 years post treatment.
Study Objectives	The goal of this study is to evaluate the safety and efficacy, in terms of Ipsilateral Breast Tumor Recurrence (IBTR) rate of cryoablation using IceCure medical's PROSENSE™ device for the treatment of low-risk early breast cancer in women 50 years or older.
Study Endpoints	Primary endpoint: Local Ipsilateral Breast Tumor Recurrence (IBTR) rate.
	Secondary endpoints:
	 Complete ablation of primary tumor rates up to 60 months after cryoablation. Improvement or maintenance of subject's quality of life at 6 months compared to baseline.

Protocol Number: ICM-BC-02

Date: Oct 27, 2021 Version:18.1

ICE3 Study – Clinical Study Synopsis

Page 2 of 3

	Breast cosmetics satisfaction.
	Regional Invasive breast tumor recurrence rate.
	Distant metastases rate including contralateral Breast cancer.
	Disease—free Survival (DFS) from date of complete ablation of the
	primary tumor, until the first disease event where the disease event
	is defined as local (DCIS or invasive), regional, or distant breast cancer
	recurrence, second primary cancer, DCIS or invasive contralateral
	breast cancer, or death due to any cause.
	Overall survival from the date of the cryoablation until the date of
	death from any cause or up to the 60 months follow up visit.
	Breast Cancer Survival from the date of cryoablation until the date of
	death from breast cancer or up to the 60 months follow-up visit.
	Subjects who died without a specified cause will be considered as
	events (i.e., due to breast cancer).
	Adverse events related to study device or procedure rate.
Study Population	Women aged 50 or older, with low-risk breast carcinoma, less or equal
	to 1.5 cm in diameter, will be enrolled into the study.
Main Eligibility	1. Diagnosis of invasive ductal breast carcinoma by core needle biopsy,
Criteria	meeting the following criteria:
	a. Unifocal primary disease
	b. Tumor size <1.5 cm in greatest diameter
	c. Nottingham grade 1-2.
	d. Estrogen receptor positive, and or progesterone receptor
	positive, HER2 negative,
	2. Age ≥ 50 (Local IRB), Age ≥ 60 (WCG IRB)
	3. Breast size adequate for safe cryoablation.
	4. Lesion must be sonographically visible at the time of treatment.
	5. History of previously treated ipsilateral or contralateral breast
	carcinoma is not an exclusion criteria if the investigator is certain
	newly diagnosed carcinoma is new unifocal primary tumor.

Protocol Number: ICM-BC-02

Date: Oct 27, 2021 Version:18.1

ICE3 Study – Clinical Study Synopsis

Page 3 of 3

Exclusion Criteria 1. Presence of lobular carcinoma 2. Presence of luminal B pathology 3. Nottingham score of 3 4. Presence of microinvasion or invasive breast carcinoma with extensive intraductal component (EIC) 5. Presence of multifocal and/or multicentric in breast cancer 6. Presence of multifocal calcifications 7. Presence of prior or concurrent neoadjuvant chemotherapy for breast 8. Presence of prior en bloc open surgical biopsy and/or lumpectomy for diagnosis/treatment of the index breast cancer 9. Patient that is not suitable to cryoablation procedure according to the physician opinion 10. ER AND PR negative, or Her2 positive noted on pre-cryo biopsy Statistical analysis-Statistical analyses will be performed using SAS® v9.3 or higher (SAS Institute, Cary NC, USA). General Statistical tests performed will be two-sided. The required significance considerations level of findings will be equal to or lower than 5%. Where the confidence level will be 95%. Baseline values are defined as the last valid value prior to study treatment start. All statistical analyses of safety and performance measures will be descriptive in nature. Continuous variables will be summarized by a mean, standard deviation, minimum, median and maximum, and categorical variables by a count and percentage. Confidence intervals will be provided where relevant. The study results will be discussed comparatively to data published of

similar products.

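### DFS is timed from complete ablation, itself a reported outcome, while overall and breast cancer survival are timed from cryoablation: align the start date and state how residual tumour counts

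*Combined protocol and SAP*

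**What the plan says.** All the relevant text is in the synopsis.

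- **Study Endpoints, DFS.** The clock is "Survival (DFS) from date of complete ablation of the" primary tumour and runs to the first disease event. The event "is defined as local (DCIS or invasive), regional, or distant breast cancer" recurrence, a second primary cancer, contralateral breast cancer or death from any cause. Residual or persistent tumour is not named.
- **Study Endpoints, complete ablation.** This is a secondary endpoint of its own: "Complete ablation of primary tumor rates up to 60 months after cryoablation".
- **Study Endpoints, survival.** The other two time-to-event endpoints start at the procedure: "Overall survival from the date of the cryoablation until the date of" death, and "Breast Cancer Survival from the date of cryoablation until the date of" death from breast cancer. Both end at the 60-month visit at the latest.
- **Study Design.** A single arm is treated, "followed by 6 month and annual mammograms and physical examinations for 5 years post treatment".
- **General considerations.** "All statistical analyses of safety and performance measures will be descriptive in nature", and results are to be discussed against published data on similar products.

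The synopsis does not define complete ablation, say how or when it is dated, equate its date with the procedure date, or say how DFS treats a woman who never reaches it.

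**The concern.** One endpoint list uses two different time origins, and one of them is an outcome that can fail or be established late. Taken literally, this has two consequences.

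1. A woman who is never completely ablated has no time zero, so she drops out of DFS. DFS then describes only women in whom treatment succeeded.
2. If completeness is dated at follow-up imaging, any death, contralateral cancer or other event before that date falls outside DFS. These women need not be ablation failures. The first scheduled follow-up is at 6 months, so the gap could be 6 months or more.

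Either way, DFS would cover a selected population on a different clock from overall survival and Breast Cancer Survival. With a single arm, no concurrent control would reveal this, and the only planned comparison is with published data, where the time origin needs to be unambiguous.

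**Working it through.** **What the text establishes.** Complete ablation is reported as a rate over a period of up to 60 months after cryoablation, so in this list it is not interchangeable with the procedure. Someone deriving DFS from the text could use either the procedure date or the date on which completeness was established. The plan states no DFS rate, ablation failure rate or DFS-based sample size, so it has no figure of its own to reproduce.

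**Inputs.** From the synopsis: 212 women, first follow-up at 6 months, horizon 60 months. Assumed, because the documents give no values:
- r, the share incompletely ablated: 2%, 5% or 10% (212 × r = about 4, 11 or 21 women).
- D, the 60-month DFS in completely ablated women: 80%, 85% or 90%.
- F, the 60-month DFS in failures: from 50% up to D.
- The DFS event list as written.

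**Effect 1: failures left out.** Overstatement = D − [(1 − r)D + rF] = r(D − F). If F = D it is 0. With F = 50%, for example, 0.10 × (90 − 50) = 4.0 points.

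**Effect 2: complete ablation dated at 6 months.** Assume a constant hazard in completely ablated women.
- Event-free at 6 months: D^(6/60) = D^0.1. The share with an event before time zero is 1 − D^0.1 = 2.2%, 1.6% and 1.0% at D = 80%, 85% and 90%, or about 2 to 5 women.
- DFS at the 60-month visit, counted from month 6: D^0.9 = 81.8%, 86.4% and 91.0%.
- Overstatement at 60 months after cryoablation: D^0.9 − D = 1.8, 1.4 and 1.0 points.

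This second effect depends on the reporting clock. Under the same constant hazard, DFS at 60 months from its own origin is D again, so the shift is 0. It is also 0 if no event occurs in the first 6 months.

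**Both together.** (D^0.9 − D) + r(D − F). The two effects do not overlap, because effect 2 is computed only in completely ablated women. For scale, take the all-treated DFS, A = (1 − r)D + rF, and the 95% half-width 1.96 × √[A(1 − A)/212], ignoring censoring. With F = 50%:

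| r | D | Effect 1 | Effect 2 | Both | A | Half-width |
|---|---|---|---|---|---|---|
| 2% | 80% | 0.6 | 1.8 | 2.4 | 79.4% | 5.4 |
| 2% | 85% | 0.7 | 1.4 | 2.1 | 84.3% | 4.9 |
| 2% | 90% | 0.8 | 1.0 | 1.8 | 89.2% | 4.2 |
| 5% | 80% | 1.5 | 1.8 | 3.3 | 78.5% | 5.5 |
| 5% | 85% | 1.75 | 1.4 | 3.1 | 83.25% | 5.0 |
| 5% | 90% | 2.0 | 1.0 | 3.0 | 88.0% | 4.4 |
| 10% | 80% | 3.0 | 1.8 | 4.8 | 77.0% | 5.7 |
| 10% | 85% | 3.5 | 1.4 | 4.9 | 81.5% | 5.2 |
| 10% | 90% | 4.0 | 1.0 | 5.0 | 86.0% | 4.7 |

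Effects and half-widths are in percentage points; sums are taken before rounding. Effect 1 alone is always inside the half-width. The combined effect exceeds it only in the last row.

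**The case against.** **It may simply mean the procedure date.** The treatment is image-guided and the lesion must be visible on ultrasound at treatment, so same-day assessment is possible. A three-page synopsis need not carry dating rules. This stands as a possibility, and the effect would then be zero. It does not settle the matter: nothing in the text equates the two dates, and the 60-month window for complete ablation points towards later assessment.

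**Starting once disease is cleared is a legitimate estimand.** A woman with residual tumour is not disease-free, and failures remain visible through the complete-ablation endpoint. This stands in part. It supports keeping DFS from complete ablation as a supplementary analysis, and it means that "overstated" is relative to an all-treated estimand. It does not justify losing early deaths or contralateral cancers in successfully ablated women, should completeness be dated late.

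**Changing the origin alone could create a new fault.** This stands in full. With the event list as written, a woman whose tumour persists could count as disease-free by default. The residual-tumour rule therefore has to be part of the change. The synopsis names the IBTR rate without saying how residual tumour is handled there, so the two rules should be settled together.

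**The size rests on assumptions.** This also stands. The figures show scale and are not estimates for this trial.

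**Conclusion.** The mismatch in time origin is certain; any distortion depends on how the phrase is applied. Under the procedure-date reading it is zero. Under the literal reading and the assumptions above, omitting failures overstates DFS by 0 to 4.0 points. Dating at 6 months adds 1.0 to 1.8 points under a constant hazard, but only if results are reported by time since cryoablation. The combined effect generally lies within the 95% half-width for 212 women. The exception is 10% failures with 90% DFS (5.0 against 4.7 points).

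A reader might infer two stronger claims that the documents do not support.
- That DFS is definitely biased: the synopsis does not say how complete ablation is dated.
- That the overstatement could reach about 9 points (r × D = 0.10 × 90): this requires every failure to be a DFS event, and the event list does not name residual tumour.

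The point is minor. DFS is a secondary, descriptive endpoint without a threshold, complete ablation is reported separately, and the primary IBTR endpoint is unaffected.

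**What to change.** Define DFS from the date of cryoablation for all treated women, as for overall survival and Breast Cancer Survival. If the procedure date was already meant, this only corrects the phrase.

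In the same change, state in the DFS event definition how residual or persistent ipsilateral tumour is counted, consistently with its handling for IBTR, so that a woman with persistent tumour is not disease-free by default. DFS from complete ablation may be kept as a labelled supplementary analysis; its dating rule and reporting clock should then be stated.

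The cost is one definition, one derivation and the residual-tumour rule. The cryoablation date is already needed for the two survival endpoints, so the start date requires no new data. Reported DFS may be less favourable.
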